A.7. Transient Cognitive Impairment in Endotoxin Model of Depression: Cognitive impairment is a common symptom of depression, experienced by two-thirds of depressed patients and associated with poor treatment response, but often overlooked by clinicians.³⁶ Low-dose endotoxin transiently impairs verbal and nonverbal memory functions in humans.²⁰ Independent preclinical data demonstrate that peripherally administered endotoxin induces memory deficit through IDO-dependent neurotoxic kynureneine metabolism; furthermore, a single peripheral injection of KYN is sufficient to induce memory deficit.⁶⁸ Notably, human studies have shown that the supplementation with branched-chain amino acids (leucine, isoleucine, and valine) has protective effects against cognitive deficits during strenuous exercises.⁶⁹⁻⁷² Based on the evidence from animal and human research, it is expected that the blockade of the BBB transport of KYN by leucine pretreatment will attenuate endotoxin-induced cognitive impairment.

A.8. Potential Impact of the Current Study and Future Directions: If the hypotheses are confirmed, the involvement of the kynureneine pathway in the induction of depressive symptoms, including cognitive impairment, will be demonstrated for the first time in a human experimental study. Furthermore, this proof-of-concept study will provide instrumental information in designing future trials of leucine to treat or prevent inflammation-associated depression. Given the minimal adverse effects and the additional benefits such as muscle mass preservation, leucine will be a prime candidate for a pharmacologic strategy to treat or prevent inflammation-associated depression.

B. INNOVATION

B.1. A highly controlled experimental model of depression to examine a novel mood mechanism

Low-dose endotoxin administration is a highly innovative experimental model to understand the causal role of inflammation in the induction of depressive symptoms; yet, it is a procedure that has only been implemented by a few laboratories in the world with only a small number of studies conducted to date (n=12).^{19,73} Using this experimental model, in addition to a randomized controlled trial design, we will evaluate the kynureneine pathway, beyond the inflammatory cascade, as a potential mechanism of inflammation-associated depression. To our knowledge, this will be the first human experimental study to evaluate the involvement of the kynureneine pathway in the induction of depressive symptoms.

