Pretreatment: Leucine is commercially available in US as dietary supplements. For this study, we will use oral preparation of the pharmaceutical grade leucine (12 g/day in 2 divided doses for 2 weeks; Ajinomoto, Raleigh, NC) mixed with effervescent powder. PO placebo will resemble the compounded mixture of leucine and effervescent powder. Clinical studies of leucine have used doses ranging from 2 to 18 g/day.⁸¹⁻⁸⁷ According to a meta-analysis, the long-term supplementation dose (i.e., 10 days to 6 months) ranged from 2.8 to 16.1 g/day with a weighted mean of 8.5 g/day.³⁰ Caspenson et al. found that leucine 12 g/day for 2 weeks improved muscle protein synthesis with a concomitant increase in phosphorylation of mechanistic target of rapamycin (mTOR) following the stimulus of a meal.⁸⁷ As this above-average dose given for 2 weeks caused increases in post-prandial protein synthesis and mTOR activation, both mechanisms also observed in preclinical studies of leucine after the stimulus of endotoxin,⁸⁸ we will use 12 g/day for 2 weeks. Participants will be given leucine or PO placebo on the day of in-person screening and will take it for 2 weeks including the morning of endotoxin administration, hence a total of 28 doses. At the end of pretreatment, subjects will indicate the presence or absence of a number of possible adverse effects in a questionnaire using a 4-point scale from 'not at all' to 'very often': symptoms include not feeling well, headache, weakness, fatigue, nausea, vomiting, burping, stomachache, bloating, flatulence, constipation, diarrhea, dry mouth, change of taste, cough, skin complaints, muscle pain, weight gain, weight loss, dizziness, sweating, and shaking. The adherence will be assessed using the Patient Adherence Questionnaire (PAQ)⁸⁹ and the count-back method (i.e., counting doses remaining in returned packets)⁹⁰ at the end of the pretreatment (i.e., immediately before endotoxin).

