C.2.4. Baseline Measures (Prior to Pretreatment): During the in-person screening session, the following measures will be assessed: sociodemographic information, sleep (DSM-5 insomnia using the SCID-5⁹² and sleep disturbance using the Pittsburgh Sleep Quality Index⁹³), depressive/anxiety symptoms (Inventory of Depressive Symptomatology⁹⁴, Beck Depression Inventory⁹⁵, Beck Anxiety Inventory⁹⁶, POMS⁶⁷, and the Montgomery-Asberg Depression Rating Scale [MADRS]⁹⁷), cognitive functions (estimated IQ using Test of Premorbid Functioning from Advanced Clinical Solutions™; verbal memory, visual memory, executive function, and attention using computerized tests from CNS Vital Signs™ including Verbal Memory Test, Visual Memory Test, Stroop Test, Shifting Attention Test, and Continuous Performance Test), systemic inflammation (CRP), and kynurenone metabolism (TRP, KYN, 3HK, QA, and KynA). Baseline measures such as sex, sleep disturbance, systemic inflammation, and KYN metabolism will be tested as potential moderators of the pretreatment effects on endotoxin-induced depression outcomes. In particular, we expect stronger effects of leucine pretreatment in females compared to males because our previous studies indicate that: 1) whereas

endotoxin increases circulating proinflammatory cytokines and IDO activity (i.e., KYN/TRP ratio) equally in males and females,^{22,53} it increases depressed mood much more robustly in females²²; 2) the correlations between cytokines and depressed mood are stronger in females²²; and 3) the correlations between IDO activity and depressed mood are stronger in females⁵³. Furthermore, before and after pretreatment, blood samples will be drawn for the assays of intracytoplasmic cytokine expression (IL-1, IL-6 and TNF- α) and nuclear signaling of inflammation (nuclear factor [NF]- κ B) using ex-vivo stimulation with endotoxin (also known as lipopolysaccharide [LPS] stimulation). These assays will measure the cellular production of cytokines in response to LPS stimulation and thus the sensitivity of peripheral blood mononuclear cells (PBMC) to an inflammatory challenge before and after pretreatment.

C.2.5. Repeated Measures (Main Study Session)

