Behavioral Measures: Depressed mood, a core symptom of depression, will be assessed immediately before endotoxin administration (T_0) and then hourly for the next 6 hours (T_1-T_6) using the POMS⁶⁷ (primary outcome). We will also use the MADRS⁹⁷ hourly (T_0-T_6) as it is sensitive to acute changes in depressed mood and anhedonia following endotoxin¹⁹ and is less oriented towards somatic symptoms than the Hamilton Depression Rating Scale. Because feelings of social disconnection and loneliness predict depression and co-occur with depressed mood following inflammatory challenge, feelings of social disconnection (Feelings of Social Disconnection Scale²¹) and loneliness (adapted UCLA Loneliness Scale⁹⁸) will also be assessed.

Participants will also complete self-report measures of sickness symptoms (e.g., muscle pain, fatigue).

Cognitive Measures: Three items from the POMS-Confusion subscale (unable to concentrate, forgetful, confused) will be assessed at T_0 and then hourly (T_1-T_6).⁶⁷ Verbal memory, visual memory, executive function, and attention be assessed at T_0 and then between T_2 and T_3 using computerized tests from CNS Vital Signs™: Verbal Memory Test, Visual Memory Test, Stroop Test, Shifting Attention Test, and Continuous Performance Test. Reichenberg et al. assessed cognitive impairment at 1, 3, and 9 hours after endotoxin and found it to be worst at 3 hours.²⁰ The order of tests will be counterbalanced across subjects to avoid any non-random version-dependent bias.⁹⁹

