The basic design is a 2 group (leucine vs. PO placebo) by 2 condition (endotoxin vs. IV placebo) independent analysis of variance (ANOVA) with one or more repeated outcome measures analyzed with linear mixed models (LMM) with primary focus upon the two endotoxin-exposed groups. The number of repeated measures varies by assessment. The key results are the main effects of pretreatment (i.e., group) while the main effects of group, condition, and their interaction will be tested. For analyses with repeated measures, the two main effects and interaction will further interact with the time variable. POMS will be the primary outcome measure. Simes correction for multiple testing will be applied for the secondary outcome measures as they are expected to be correlated.¹¹⁰

C.2.9. Justification of Sample Size

The effect sizes for the reduction of endotoxin-induced depressive symptoms by leucine within the animal data are very large ($d=.90$), but we have assumed some attenuation in humans ($d=.70$). Assuming an effect of this size, with $n=35$ per group, there is >80% power to detect differences between the leucine and PO placebo pretreatments with endotoxin exposure for the single time point outcomes (e.g., Cyberball Social Exclusion); comparisons for repeated measures assessments will have more power (>90%) and able to detect more subtle effects at >80% power. Both 'leucine + IV placebo' and 'PO placebo + IV placebo' arms are expected to show minimal depression with means over time to be very near zero but exist as reference points to the endotoxin condition, which our previous work suggests to have large effects. With repeated measures, $n=10$ can detect

medium sized effects ($d=.50$) with power $>80\%$. Thus, there is more than adequate power with 35 vs. 10 to show the effect of endotoxin exposure within pretreatment groups.

REFERENCES

3. Depression Guideline Panel: Clinical Practice Guideline 5: Depression in Primary Care, vol 2: Treatment of Major Depression. In: US Department of Health and Human Services PHS, Agency for Health Care Policy and Research, ed. Rockville, MD. 1993.

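### The pre-drug scores on the Aim 3 cognitive tests have no role in the planned model; adding them as a covariate buys precision, by an amount that depends on the contrast

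*Combined protocol and SAP*

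**What the plan says.** Section C.2.4 lists, at the in-person screening session before pretreatment, "verbal memory, visual memory, executive function, and attention using computerized tests from CNS Vital Signs" and "estimated IQ using Test of Premorbid Functioning from Advanced Clinical Solutions". Study drug starts the same day: "Participants will be given leucine or PO placebo on the day of in-person screening" (C.2.3).

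Section C.2.5 (Cognitive Measures) brings back the same five tests in the main session, to "be assessed at T_0 and then between T_2 and T_3 using computerized tests from CNS Vital Signs". T0 is immediately before endotoxin, after about two weeks on study drug.

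Section C.2.8 describes a 2 by 2 design (pretreatment by endotoxin condition), analysed by linear mixed models where the outcome is repeated, with primary attention to the two endotoxin arms. It states: "The key results are the main effects of pretreatment (i.e., group) while the main effects of group, condition, and their interaction will be tested". These terms are also crossed with time. No baseline covariate is named. The only adjustment stated is for sickness symptoms (C.2.7). Baseline measures are given one use, in C.2.4: "Baseline measures such as sex, sleep disturbance, systemic inflammation, and KYN metabolism will be tested as potential moderators of the pretreatment effects". That sentence concerns depression outcomes, and its list names neither cognition nor IQ.

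**The concern.** A pre-treatment value of the outcome is usually the strongest covariate available. Here it is collected for all five Aim 3 tests and then has no stated place in their analysis. T0 cannot fill that place for leucine vs placebo, because by then leucine has been taken for about two weeks and T0 is itself a possible outcome of pretreatment.

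The effect C.2.8 calls key is the group main effect. Averaged over T0 and T2-T3, it keeps stable differences in ability between participants in its error. The Aim 3 tests are secondary outcomes that must also pass the Simes correction, so avoidable noise matters. A model without the screening score also leaves it unclear how an effect of leucine before endotoxin would be told apart from an effect on the response to endotoxin.

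**Working it through.** **Inputs from the plan (C.2.9):** 35 per endotoxin arm and d=.70, which the plan derives from depressive symptoms; it gives no cognitive effect size.

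**Assumed, because the plan does not state them:** two-sided 0.05, no dropout, unit variance at each occasion, and one common correlation ρ among the screening, T0 and T2-T3 scores. Only the two endotoxin arms are compared.

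**Power:** noncentral t with noncentrality e·√(35/2), where e is the standardised effect of the contrast. There are 68 degrees of freedom, less one per covariate.

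**The plan's own figure.** For one score, e=.70 gives 82.3%. The stated figure above 80% for single time point outcomes reproduces.

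**1. Group effect averaged over T0 and T2-T3.** The variance is (1+ρ)/2. Its covariance with the screening score is ρ, so the adjusted variance is (1+ρ)/2 − ρ².
- ρ=0.5: 0.75 falls to 0.50.
- ρ=0.7: 0.85 falls to 0.36.

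The averaged effect is .70 if leucine acts equally at both occasions. It is (0+.70)/2 = .35 if leucine acts only after endotoxin.

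| Case | ρ | e without → with screening | Power without → with |
|---|---|---|---|
| Both occasions | 0.3 | .868 → .935 | 94.7% → 97.1% |
| Both occasions | 0.5 | .808 → .990 | 91.5% → 98.3% |
| Both occasions | 0.7 | .759 → 1.167 | 87.9% → 99.8% |
| After endotoxin only | 0.3 | .434 → .468 | 43.3% → 48.7% |
| After endotoxin only | 0.5 | .404 → .495 | 38.5% → 53.2% |
| After endotoxin only | 0.7 | .380 → .583 | 34.7% → 67.2% |

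Screening is two weeks earlier, so it may correlate less with the main session than the two same-day scores do with each other. With 0.6 for screening and 0.7 between T0 and T2-T3, the adjusted variance is 0.85 − 0.36 = 0.49. Power is then 98.5% (both occasions) and 54.1% (after endotoxin only).

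**2. T2-T3 score alone.** e = .70/√(1−ρ²). Power rises from 82.3% to 85.7% (ρ=0.3), 91.5% (0.5) or 98.1% (0.7).

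**3. T2-T3 score with T0 already a covariate, and no leucine effect at T0.** The residual variance falls from 1−ρ² to 1−2ρ²/(1+ρ).
- ρ=0.5: 0.750 to 0.667, power 91.5% to 94.2%.
- ρ=0.7: 0.510 to 0.424, power 98.1% to 99.3%.

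The gain is about 1 to 3 points.

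**4. Group-by-time (change from T0).** The covariance of the change with screening is ρ−ρ = 0, so the gain is nil. With no leucine effect at T0, e = .70/√(2(1−ρ)), and power is 82.3% at ρ=0.5 and 96.1% at ρ=0.7 with or without the screening score.

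**The case against.** The strongest reply is that the plan already handles much of this. The tests are repeated, T0 is in the mixed model, and group-by-time removes stable differences between people. For that contrast the screening score adds nothing, and change from T0 does well at higher correlations (96.1% at ρ=0.7). This stands. A reader might infer from case 2 that Aim 3 as a whole loses 9 to 16 points of power (82.3% against 91.5% to 98.1%). The documents do not support that. The figure belongs to a lone T2-T3 score at a correlation the plan does not give, while C.2.8 puts repeated outcomes in a model with time, and C.2.9 claims more than 90% power for them.

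It can also be said that Aim 3 asks about responses to endotoxin, so T0 is the proper reference. That stands too, and it is why the T0-based comparison should not be replaced by a T2-T3 score adjusted for screening alone: that would mix any leucine effect already present at T0 into the result.

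A reader might further infer that leucine is expected to have changed cognition by T0, since A.7 says that "human studies have shown that the supplementation with branched-chain amino acids (leucine, isoleucine, and valine) has protective effects against cognitive deficits". The sentence goes on to limit this to strenuous exercise, so it is weak support for an effect at rest. A T0 effect is possible, not shown.

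Finally, C.2.8 is silent on baseline covariates and excludes none, and the moderator list in C.2.4 is open-ended. The fault is therefore one of specification. But the averaged group effect, which C.2.8 calls key, does gain, and none of these replies is a reason to leave the screening score out.

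**Conclusion.** The point holds as one of precision and pre-specification for secondary outcomes. The analysis would not be biased without the screening scores, because allocation is random. Nor is a pre-drug reference missing from the data: the scores are collected and only lack a role in the model.

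At ρ of 0.5 to 0.7 the gain in power is about 7 to 12 points for the averaged group effect if leucine acts at both occasions, and about 15 to 33 points if it acts only after endotoxin. At ρ=0.3 these gains shrink to 97.1 − 94.7 = 2.4 and 48.7 − 43.3 = 5.4 points. They are 1 to 3 points where T0 is already a covariate, and nil for group-by-time. All of these figures rest on an assumed correlation, an assumed two-sided 0.05, and an effect size borrowed from depressive symptoms. The ordering of the contrasts is more secure than any single percentage.

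**What to change.** In C.2.8, for each CNS Vital Signs outcome, add the same test's screening (pre-pretreatment) score as a covariate in the planned linear mixed model. Keep T0 and T2-T3 as the repeated outcomes. From that model, report the leucine vs PO placebo difference at T0 and at T2-T3, so that an effect present before endotoxin is shown apart from the response to endotoxin.

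The cost is a sentence or two in C.2.8 and one degree of freedom per model. No new data, visits or participants are needed. The text should be settled before unblinding.

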C.1.3. Endotoxin induces changes in KYN metabolism, which correlates with depressed mood

[figure not shown]

Fig. 5 Leucine reduces brain KYN:TRP ratios and blocks depression-like behavior. **A,B** Mean sucrose preference (%) and time spent immobile in the forced swim test (s) (\pm SEM) of mice treated with leucine or vehicle immediately before and 6 h after LPS or phosphate-buffered saline (PBS) ($n > 14$ per group). **C,D** Mean KYN:TRP ratios in plasma and brains (\pm 442 SEM) of mice treated with 50 mg/kg leucine or vehicle immediately before and 6 h after LPS or PBS ($n = 5$ per group).

** $p < 0.01$, *** $p < 0.001$ for LPS vs. PBS main effects. * $p < 0.05$, ** $p < 0.01$, *** $p < 0.001$ for leucine vs. vehicle main effects.

Aim: In the aforementioned study in C.1.2. (N=115), we examined whether endotoxin induces changes in kynurenine metabolism and whether these changes correlate with inflammation-induced depressed mood.

Methods: Circulating kynurenine metabolites (TRP, KYN, QA, KynA) were measured at T₀, T₂, and T₆. The primary outcome was IDO activity assessed using KYN/TRP. **Results:** Participants exposed to endotoxin (vs. placebo) showed greater increases in IDO activity (p<0.0001). Among endotoxin-exposed participants (N=61; 38 females), the correlation between IDO activity and depressed mood was highly significant (p=0.004).

Conclusion: Inflammatory challenge increased IDO activity, which in turn was significantly correlated with inflammation-induced depressed mood. *These data confirm endotoxin-induced increases in peripheral conversion of TRP to KYN as well as increases in depressed mood, and thus show the feasibility of inhibiting blood-to-brain transport of KYN as well as inflammation-induced depressed mood.*

C.2. Research Design and Methods

C.2.1. Overview of Study Design (Fig. 6):

In this double-blind randomized placebo-controlled four-arm study, a total of 90 healthy volunteers (ages 18-65) will be randomly assigned to a two-week pretreatment of L-leucine (hereafter referred to as leucine) or PO placebo (i.e., maltodextrin). After the pre-treatment period, they will receive low-dose endotoxin or IV placebo (i.e. saline): n₁=35 leucine + endotoxin; n₂=35 PO placebo + endotoxin; n₃=10 leucine + IV placebo; n₄=10 PO placebo + IV placebo. (see Justification of Sample Size for the rationale for smaller IV placebo arms)

[figure not shown]

Fig. 6 Overview of study design

C.2.2. Subjects:

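### Sex is said to drive the mood response to endotoxin, but neither sex nor screening POMS is in the stated model, and no balancing on sex is described

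*Combined protocol and SAP*

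**What the plan says.** C.2.4 (Baseline Measures) reports from the investigators' earlier work that, although cytokines and IDO activity rise equally in both sexes, endotoxin affects mood differently: "it increases depressed mood much more robustly in females". It goes on: "we expect stronger effects of leucine pretreatment in females compared to males". Sex is then listed with sleep disturbance, inflammation and kynurenine measures as a potential moderator. The same section places POMS among the measures taken at in-person screening, before pretreatment. No analysis use is given for that score.

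C.2.1 says that participants "will be randomly assigned to a two-week pretreatment" of leucine or placebo and gives arm sizes of 35, 35, 10 and 10. It names no stratification factor, blocking or minimisation.

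C.2.8 builds the model from group, condition and their interaction. For repeated outcomes, "the two main effects and interaction will further interact with the time variable". It calls the main effects of pretreatment the key results and puts the primary focus on the two endotoxin arms. No baseline covariate is listed. The only adjustment named anywhere is for sickness symptoms (C.2.7), which arise after randomisation.

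On power, C.2.9 assumes d = .70 and says that, for outcomes measured once, "with $n=35$ per group, there is >80% power to detect differences between the leucine and PO placebo pretreatments" under endotoxin. It claims more than 90% for repeated measures.

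**The concern.** The plan treats sex as a strong predictor of the primary outcome and as a likely modifier of the treatment effect, then leaves it out of the model that estimates that effect. The moderator test does not adjust the primary contrast.

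Two things follow. Variance that sex and screening POMS could explain stays in the error term. And if one endotoxin arm happens to hold more women, the unadjusted leucine contrast moves with that imbalance. Screening POMS matters here because it is the only pre-treatment value of the primary outcome: the T0 score in C.2.5 is taken after two weeks of leucine or placebo.

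**Working it through.** **Inputs from the plan.** d = .70 and 35 per endotoxin arm (C.2.9); POMS at T0 and hourly T1 to T6 (C.2.5); 69 of 115 participants (60%) female in the earlier study (C.1.2).

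**Assumptions, because the plan gives no figure.** Two-sided alpha .05; simple randomisation; 50% or 60% female; sex gap in response 0.5 to 1.0 SD; covariate R² .05 to .25; within-person correlation .5 to .9.

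**1. The plan's own figure.** Two-sample t test, 35 per arm, d = .70, noncentrality .70 × √(35/2) = 2.93, 68 df: power 82.3% (normal approximation 83.4%). The stated figure of more than 80% for single-time-point outcomes reproduces.

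**2. Chance sex imbalance, 35 against 35.**
- SD of the difference in proportion female at 50% female: √(2 × .5 × .5/35) = .120.
- Chance of a difference of 20 points or more (7 people or more), independent binomials: 12.0% at 50% female, 11.2% at 60%. With the total number of women held fixed (35 or 42 of 70), it is 15.1% or 8.7%.

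**3. What the imbalance does.** Shift = sex gap × imbalance.
- 20 points: 0.5 × .20 = 0.10 SD; 1.0 × .20 = 0.20 SD. That is 14% to 29% of .70.
- A typical (1-SD) imbalance: 0.5 × .12 = 0.06 SD; 1.0 × .12 = 0.12 SD. The standard error of the contrast is √(2/35) = 0.24 SD.
- If a 20-point imbalance is unfavourable, the effect seen falls to .60 or .50 SD, and single-time-point power to 70% or 54%.

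**4. Precision, outcomes measured once (for example Cyberball).** Adjusted effect = .70/√(1 − R²), 66 df; equivalent unadjusted size = 35/(1 − R²).
- R² .05: .718, power 84.1%, 36.8 per arm.
- R² .10: .738, power 86.0%, 38.9 per arm.
- R² .25: .808, power 91.5%, 46.7 per arm.

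In a 50:50 sample, sex alone explains .25 × gap²: 6% for a gap of 0.5 SD and 25% for 1.0 SD.

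**5. Precision, mean of six post-dose POMS values.** With compound symmetry at correlation ρ, effect = .70/√((1 + 5ρ)/6).

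| ρ | Effect | Power, unadjusted | R² .09 | R² .25 |
|---|---|---|---|---|
| .5 | .917 | 97% | 98% | 99% |
| .7 | .808 | 92% | 94% | 97% |
| .9 | .731 | 85% | 88% | 94% |

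**6. Does the moderator test cover this?** With equal sexes, the standard error of a sex difference in effect is √(4/17.5) = 0.478 SD. A difference as large as 0.7 SD then has about 31% power (normal approximation). The test is weak, and it does not alter the primary estimate.

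**The case against.** The case against has real force.

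- **Power.** A reader might infer that the primary comparison has only 82% power. The documents do not support that. C.2.9 ties that level to outcomes measured once and claims more than 90% for repeated measures such as POMS. At correlations up to about .7 the gain for POMS is 1 to 6 points on power already above 90%.
- **Bias.** A reader might also infer a biased estimate. Randomisation makes the expected shift zero, and the ordinary standard error already allows for chance imbalance. Imbalance and lost precision are partly the same cost.
- **Small arms.** Chance imbalance between the two 10-person arms looks alarming but matters little. They are reference arms expected near zero, and the sex effect described is a response to endotoxin.
- **Silence.** C.2.1 gives no allocation mechanics, so simple randomisation is not established; the 12% depends on it.
- **Form of adjustment.** A time-constant covariate subtracts out of a group × time contrast with complete data, so a plain sex term would leave that contrast unchanged. This is correct and shapes the fix. But C.2.8 calls the group main effects the key results, and those benefit from adjustment, as do the tasks done only once at T2. Using T0 as a reference does not remove a sex imbalance in the response to endotoxin.
- **Screening POMS.** No passage says that it predicts the response. C.2.2 excludes PHQ-9 of 5 or more, so scores may sit near the floor. Its contribution may be small.

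**Conclusion.** The point holds as one of efficiency and robustness. The plan names a strong predictor of its primary outcome, collects it before treatment, and leaves it out of the stated model, with no balancing on it described. It does not show systematic bias, and it does not make the stated power wrong.

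The size is moderate and rests on assumptions, since the documents give no sex difference, no R² and no within-person correlation. Under the ranges used, a 20-point sex imbalance moves the leucine contrast by 0.10 to 0.20 SD in either direction, and the typical shift is smaller, at 0.06 to 0.12 SD. Adjustment is worth about 2 to 9 percentage points of power for outcomes measured once. For the six-value POMS mean it takes a range of 85–97% to 88–99%, with the larger gains where the repeated values are highly correlated. The argument is stronger for sex, where it rests on the plan's own statement, than for screening POMS.

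**What to change.** Amend C.2.8, before unblinding, to prespecify baseline covariates for every leucine contrast:

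- **Repeated outcomes:** sex with sex × time, and screening POMS with screening POMS × time. In the four-arm model add sex × condition and sex × condition × time, because the sex difference described is in the response to endotoxin.
- **Outcomes measured once at T2:** sex and screening POMS as simple covariates.

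Amend C.2.1 to state the allocation method and to stratify any remaining allocation by sex. Permuted blocks in the ratio 7:7:2:2 (block of 18) match 35:35:10:10. An incomplete last block in either stratum could leave arm totals slightly off target.

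Naming group × sex within the endotoxin arms as the lead moderator is optional emphasis.

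The cost is a revised randomisation list for participants still to be enrolled and a few more model terms. No new data are needed. If enrolment is complete, the covariate part can still be adopted. If screening POMS proves uninformative, it costs only a few degrees of freedom.
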